## 1 Introduction

This Primary Statistical Analysis Plan (SAP) outlines the general statistical approaches that will be used in the primary statistical analysis of NICHD P1091. The focus is on analyses that address the study's primary and secondary objectives, as well as summaries of the primary and secondary outcome measures that will be posted on ClinicalTrials.gov. It will facilitate discussion of the statistical analysis components among members of the study team and provide agreement between the team and statistician regarding the analyses to be performed and presented in the primary statistical analysis report. Detailed outlines of tables and coding descriptions that will be included in the primary statistical analysis report are included in the Analysis Implementation Plan (AIP).

Analyses for the primary statistical report will be initiated once the last participant has completed the last study visit, all laboratory data are available, all queries have been resolved, and the database has been frozen for analysis. This report will be used for submission of results to ClinicalTrials.gov. Results are required to be submitted within one year of the primary completion date (PCD), which is the date the last participant is examined for the purposes of data collection for the primary outcome measure. For this study, the PCD is based on the last study visit.

## 2 Key Updates to the SAP

N/A

## 3 Protocol Overview

### 3.1 Study Design

**DESIGN:** A double-blind, randomized, placebo-controlled study to evaluate the safety and immunogenicity of two pneumococcal vaccines in HIV-infected pregnant women in their second or third trimester on highly active antiretroviral therapy (HAART) and their infants.

**SAMPLE SIZE:** Approximately 345 Human Immunodeficiency Virus (HIV)-infected pregnant women and their 345 infants (690 participants), equally distributed among three treatment arms to obtain  $\geq 100$  evaluable pairs/arm (300 total pairs, or 600 total participants).

**REGIMEN:** **Step 1.** Pregnant women will be randomized between  $\geq 14$  weeks (14 weeks 0 days) to  $< 33$  weeks (32 weeks 6 days) of gestation to one of three blinded treatment arms (administered on Day 0):

- Arm 1A: pneumococcal polysaccharide 23-valent vaccine (PPV-23);
- Arm 1B: pneumococcal conjugate 10-valent vaccine (PCV-10); or
- Arm 1C: placebo.

**Step 2.** Women randomized to Arm 1C (placebo) who complete Step 1 will be screened for entry into Step 2 and will be randomized to receive PPV-23 (Arm 2A) or PCV-10 (Arm 2B) at 24 weeks after delivery. The women who received active vaccine during pregnancy (Arms 1A and 1B) will stop study at 24 weeks after delivery.

**Step 3.** Women who were initially randomized to Arm 1C and meet an exclusion criterion for Step 2 due to new pregnancy will be enrolled in Step 3 and receive open label PCV-10 at the last study visit (which coincides with Step 1 24 weeks post-delivery).

All infants will receive PCV-10 per local standard of care.

STUDY DURATION: Up to 60 weeks for women (approximately 28 weeks pre-delivery; 32 weeks post-delivery) and up to 28 weeks for infants.

### 3.2 Study Objectives and Outcome Measures

#### Primary objectives and outcome measures:

1. To assess the safety of the PCV-10 and PPV-23 vaccines in HIV-infected pregnant women on HAART.

- Outcome measures:

#### Maternal:

- Grade  $\geq 3$  AEs up to 4 weeks after vaccination (in Steps 1 and 2)
- Grade  $\geq 3$  AEs judged to be related to the study treatment (in Steps 1 and 2) throughout the study
- Grade 4 AEs or death after week 4 after vaccination (in Step 1)

#### Neonatal:

- Grade  $\geq 3$  AEs
- Congenital defects

- HIV infections
- Pneumonia or IPD

2. To compare the immunogenicity of PCV-10 with PPV-23 vaccines in HIV-infected pregnant women on HAART.
  - Outcome measure:
    - Raw values and fold change in ELISA-measured IgG PNC antibody concentrations from baseline to week 4 in Step 1 to  $\geq 1$  serotype. Serotypes measured by ELISA are: 1, 4, 5, 6B, 7F, 14, 23F and 33F.
3. To compare the level of Pneumococcal (PNC) antibodies at 8 weeks of life in infants born to mothers who received PCV-10 or PPV-23 vaccines.
  - Outcome measures:
    - ELISA-measured IgG PNC antibody levels  $\geq 0.35\text{ug/mL}$  at 8 weeks of age for  $\geq 1$  serotype from those listed above.

Secondary objectives and outcome measures:

1. To compare the level of transplacentally transferred vaccine-serotype PNC antibodies in infants born to mothers who received PCV-10 or PPV-23 versus placebo.
  - Outcome measure: Average ratio of infant/mother ELISA-measured IgG PNC antibody levels across the serotypes listed above, measured at birth/delivery
2. To compare the immunogenicity of PCV-10 and PPV-23 vaccines with placebo in HIV-infected pregnant women on HAART.
  - Outcome measure: ELISA-measured IgG PNC antibody concentrations at week 4 in Step 1, in all treatment groups
3. To compare the persistence of vaccine-serotype PNC anti-capsular antibodies for up to 24 weeks after delivery in HIV-infected women vaccinated with PCV-10, PPV-23 or placebo.
  - Outcome measure: ELISA-measured IgG PNC antibody concentrations at labor&delivery and week 24 post-delivery in Step 1, in all treatment groups
4. To compare maternal antibody responses to PPV-23 or PCV-10 administered during pregnancy with responses to PPV-23 or PCV-10 administered 24 weeks postpartum.
  - Outcome measure: ELISA-measured IgG PNC antibody concentrations at week 4 in

Step 1 and at week 4 in Step 2, in the women who received PPV-23 or PCV-10

5. To evaluate the effect of the following factors on the magnitude and persistence of the maternal antibody responses to PCV-10 and PPV-23: maternal age, ethnicity, cluster of differentiation 4 (CD4), cluster of differentiation 8 (CD8), plasma HIV RNA and gestational age at immunization.
  - Outcome measure: ELISA-measured IgG PNC antibody concentrations at week 4 in Step 1, in the women who received PPV-23 or PCV-10, and the following variables (measured at week 0):
    - maternal age,
    - ethnicity,
    - cluster of differentiation 4 (CD4),
    - cluster of differentiation 8 (CD8),
    - plasma HIV RNA and
    - gestational age.
6. To assess potential interference of maternal antibodies with infant vaccine-serotype PNC anti-capsular antibody responses after the first 2 doses of PCV-10 and determine if interference of maternal antibodies differs in PCV-10 from PPV-23 and from placebo recipients.
  - Outcome measure: ELISA-measured IgG PNC antibody concentrations at weeks 16 and 24 in infants

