#### Infant Schedule:

Study visits for infants were conducted at birth (with a window of +7 days), week 8, which should be  $\leq 7$  days before the 1st dose of PCV-10 (with a window of +14 days), week 16, which should be  $\leq 7$  days before the 2nd dose of PCV-10 (with a window of  $\pm 28$  days), week 24, which

should be  $\geq$  28 days after the 2nd dose of PCV-10 (with a window of 28 days), or for Invasive Pneumococcal Disease (IPD).

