### Infants:

This is an as-treated analysis including only the infants born to women who have been vaccinated and those who have received the PCV-10 vaccination prior to the week 8 study visit.

Summaries will include the proportion (%) and 95% CI of infants born to mothers who received PCV-10 or PPV-23 vaccines who had ELISA-measured IgG PNC antibody levels  $\geq 0.35\mu\text{g/mL}$  at 8 weeks of age for  $\geq 1$  serotype listed above. The difference in proportions between the two groups will be assessed using a Chi-Square test.

In the case of twins, one child will be chosen at random for the primary immunogenicity analysis. Sensitivity analyses will repeat these summaries in the event that twins are enrolled in the study, re-doing the analysis using the other sibling.

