## 5.4 Secondary Objectives

Summaries will include:

- i) means (or medians if data are not normally distributed) and 95% CI of mean ratio of infant/mother ELISA-measured IgG PNC antibody levels across the serotypes listed above, measured at birth/delivery;
- ii) Summary table with proportion (%) and 95% CI of women in the each treatment group who had a  $\geq$ two-fold increase to each serotypes in ELISA-measured IgG PNC antibody concentrations from baseline to week 4 after immunization in Step 1;
- iii) Summary table with proportion (%) and 95% CI of women by treatment arm who had ELISA-measured IgG PNC antibody levels  $\geq 0.35\text{ug/mL}$  at week 4 after immunization in Step 1, at labor&delivery, and at week 24 post-delivery in Step 1 to  $\geq 1$  of the serotypes listed above;
- iv) Summary table with proportion (%) and 95% CI of women who had a two-fold increase to  $\geq 1$  serotype in ELISA-measured IgG PNC antibody concentrations from baseline to week 4 after immunization in Step 1 vs the women who achieved this from entry to Step 2 until week 4 post immunization in Step 2 (for each of the two vaccines). The analyses will exclude the women who delivered prior to week 4 in Step 1;
- v) Correlations between ELISA-measured IgG PNC antibody concentrations at weeks 4 in Step 1, in the women who received PPV-23 or PCV-10, and the following variables (measured at week 0): maternal age, ethnicity, cluster of differentiation 4 (CD4) count, cluster of differentiation 8 (CD8) count, plasma HIV RNA and gestational age;
- vi) Summary table with proportion (%) and 95% CI of infants born to mothers who received PCV-10 or PPV-23 vaccines who had ELISA-measured IgG PNC antibody levels  $\geq 0.35\text{ug/mL}$  at 16 and 24 weeks of age for  $\geq 1$  serotypes listed above;
- vii) Summary table with mean (95% CI) number of serotypes with levels  $\geq 0.35\text{ug/mL}$  at weeks 16 and 24 of age in study infants.

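### Secondary objective 1 asks about infant antibody level versus placebo, but its only measure is the infant/mother ratio, and no summary gives placebo infants' levels before infant vaccination

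*SAP*

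**What the plan says.** SAP section 3.2 words secondary objective 1 as: "To compare the level of transplacentally transferred vaccine-serotype PNC antibodies in infants born to mothers who received PCV-10 or PPV-23 versus placebo". One outcome measure is attached to it: "Average ratio of infant/mother ELISA-measured IgG PNC antibody levels across the serotypes listed above, measured at birth/delivery". The matching analysis, section 5.4 item i, gives means or medians with a 95% CI of the "mean ratio of infant/mother ELISA-measured IgG PNC antibody levels across the serotypes listed above, measured at birth/delivery". It names no arms and no contrast with placebo.

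The other infant antibody summaries are these:

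- Section 5.3, Infants (week 8): "Summaries will include the proportion (%) and 95% CI of infants born to mothers who received PCV-10 or PPV-23 vaccines", with a test between those two groups.
- Section 5.4 item vi (weeks 16 and 24): "Summary table with proportion (%) and 95% CI of infants born to mothers who received PCV-10 or PPV-23 vaccines".
- Section 5.4 item vii: the mean number of serotypes at or above the threshold "at weeks 16 and 24 of age in study infants".

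Section 5.1 places the week 8 visit before the first infant PCV-10 dose, week 16 before the second dose and week 24 after it. Section 3.1 has all infants receiving PCV-10.

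**The concern.** The objective and its measure address different quantities. The objective concerns the amount of antibody the infant holds, compared with placebo. The measure is the infant's amount as a fraction of the mother's. A vaccine that raises the maternal level and leaves transfer efficiency unchanged raises the infant level in proportion, yet the ratio is the same in every arm. If transfer is less efficient at high maternal levels, the ratio falls with vaccination while the infant level rises.

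Section 1 says that summaries of the secondary outcome measures will be posted on the public registry. An equal or lower ratio, reported against an objective about infant level, could be read as no gain for the infant, or as harm, when infants in fact hold more antibody.

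**Working it through.** The SAP gives no effect size, SD or power for this objective, so there is no planned figure to reproduce. The check has three parts.

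**1. Every planned infant antibody summary**

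| Visit | Relation to infant PCV-10 | Quantity | Placebo infants included? |
|---|---|---|---|
| Birth (5.4 i) | before dose 1 | infant/mother ratio only | arms not stated |
| Week 8 (5.3) | before dose 1, per 5.1 | proportion ≥0.35 µg/mL, ≥1 serotype | no |
| Weeks 16 and 24 (5.4 vi) | after dose 1 is due; week 24 after dose 2 | proportion ≥0.35 µg/mL, ≥1 serotype | no |
| Weeks 16 and 24 (5.4 vii) | as above | number of serotypes ≥0.35 µg/mL | possibly |

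Section 5.4 item iii includes delivery but is maternal. Summaries of the antibody level of placebo infants before infant vaccination: 0.

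**2. Level versus ratio**

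For one serotype on the geometric scale, infant level = maternal level × ratio. Let F be the maternal level with vaccine divided by that with placebo, and r the transfer ratio with vaccine divided by that with placebo. Then:

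- fold difference in infant level = F × r
- fold difference in infant/mother ratio = r
- the two move in opposite directions whenever 1/F < r < 1

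F and r are assumed, because the SAP gives neither.

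| F | r | Infant level, vaccine/placebo | Infant/mother ratio, vaccine/placebo |
|---|---|---|---|
| 2 | 1 | 2 | 1.00 |
| 4 | 1 | 4 | 1.00 |
| 8 | 1 | 8 | 1.00 |
| 2 | 0.60/0.80 = 0.75 | 1.5 | 0.75 |
| 4 | 0.75 | 3 | 0.75 |
| 8 | 0.75 | 6 | 0.75 |

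For F = 2, 4 and 8, opposite directions occur for r between 0.5, 0.25 or 0.125 and 1.

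The same point can be put as power for a two-sample comparison on the log scale. This assumes 100 pairs per arm (300/3, section 3.1), two-sided 0.05, SD 1.0 for ln infant level and SD 0.5 for ln ratio. Both SDs are assumed, and item i itself names no test.

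- F = 2, r = 1: infant level differs 2-fold. Power is 99.8% on level; the ratio comparison rejects at its 5% error rate.
- F = 2, r = 0.8: infant level is 2 × 0.8 = 1.6 times higher, with power 91.4%. The ratio comparison has 88.4% power in the opposite direction.
- F = 2, r = 0.5: infant levels are identical (2 × 0.5 = 1), yet the ratio comparison rejects almost always.

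**3. Precision of the missing comparison**

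With 100 infants per arm and SD s of the log concentration, the 95% CI of a vaccine/placebo geometric mean ratio runs from the estimate divided by k to the estimate times k, where k = exp(1.96 × s × √(2/100)) = exp(0.277 × s):

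- s = 0.75: k = 1.23
- s = 1.0: k = 1.32
- s = 1.25: k = 1.41

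The values of s are assumed, and all 100 evaluable pairs per arm are taken to have usable birth samples.

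**The case against.** The best defence is that level of transferred antibody can be read as extent of transfer, which an infant/mother ratio at birth does measure. On that reading the fault is one of wording. But the SAP elsewhere uses level for a concentration: primary objective 3, also about infant level, is assessed against 0.35 µg/mL, and the ratio itself is described as a ratio of levels. Either way the text must change.

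Second, section 1 leaves detailed table outlines to the Analysis Implementation Plan, which is not at hand and might tabulate the infant birth concentration. That limits the claim to what the SAP names. It does not remove the point, because the SAP fixes the outcome measure and says it focuses on analyses that address the secondary objectives.

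Third, secondary objective 3 covers maternal concentration at delivery in all arms, which read with the ratio hints at infant level. This is partial help: section 5.4 item iii reports only the proportion of mothers above the threshold for at least one serotype. The general sentence in section 5 on chi-square tests against placebo attaches no infant outcome or visit.

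Two technical cautions stand. The F × r identity is exact for one serotype on the geometric scale, or under a common r, whereas the planned statistic is a mean or median of a ratio averaged over eight serotypes. The fold figures therefore show direction and rough size; they do not predict that statistic. And eight serotypes by two vaccines give 8 × 2 = 16 contrasts, which section 5 leaves unadjusted.

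**Conclusion.** The concern holds. As written, the SAP does not answer secondary objective 1: the measure is transfer efficiency, and no named summary gives placebo infants' antibody level before infant vaccination. That conclusion rests on the text and on the identity between level and ratio, not on the assumed values. The size is illustrative: with equal transfer the ratio shows no difference while infant level may be 2, 4 or 8 times higher, and with r = 0.75 the ratio is 25% lower while infant level is 1.5, 3 or 6 times higher. One secondary objective is affected and the primary analyses are not. It should be corrected before the results are reported.

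**What to change.** Add to secondary objective 1 and to section 5.4 item i the infant IgG concentration at birth for each serotype, as a geometric mean with 95% CI, by maternal arm including placebo. Give the geometric mean ratios of PCV-10 and of PPV-23 to placebo with 95% CIs, and state that these 16 contrasts are descriptive and unadjusted. Keep the infant/mother ratio beside them, by arm, labelled as transfer efficiency.

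A smaller change would extend the 0.35 µg/mL proportion to placebo infants at birth or week 8. It matches the SAP's other infant summaries but loses the size of the difference.

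If only transfer efficiency was intended, reword the objective to say so and name the comparison with placebo.

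The cost is one table and one added secondary measure, which would also enter the posted outcome measures. No new samples are needed, because the infant birth concentration is already the numerator of the planned ratio. If the team has already seen post-entry data, section 5 requires the addition to be labelled post hoc.

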## 5 Statistical Methods

Baseline characteristics will be summarized by treatment group but with no statistical comparisons comparing arms.

Statistical tests will not be adjusted for interim monitoring or multiple comparisons. The Chi-square tests will be used to compare rates of response following vaccination between the vaccinated groups and placebo group. The statistical tests will be two-sided with a nominal significance level of 0.05. Categorical data will be summarized using N (%) and 90% or 95% confidence intervals (CIs), and continuous data using N, min, Q1, median, Q3, max, and mean (STD) (when appropriate) and 95% CI.

Any modifications to outcome measures after the team has seen data collected after entry will be identified as *post hoc* in the analysis report.

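### Secondary objective 1 averages raw infant/mother antibody ratios; geometric mean ratios would remove an upward pull of unknown size

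*SAP*

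**What the plan says.** SAP section 3.2 states secondary objective 1 as "To compare the level of transplacentally transferred vaccine-serotype PNC antibodies in infants born to mothers who received PCV-10 or PPV-23 versus placebo". Its outcome measure is "Average ratio of infant/mother ELISA-measured IgG PNC antibody levels across the serotypes listed above, measured at birth/delivery". The serotypes are given in the same section under the primary immunogenicity objective: "Serotypes measured by ELISA are: 1, 4, 5, 6B, 7F, 14, 23F and 33F". That is eight ratios per mother-infant pair.

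Section 5.4, item i, plans the summary as "means (or medians if data are not normally distributed) and 95% CI of mean ratio of infant/mother ELISA-measured IgG PNC antibody levels", again taken across the serotypes. The general rule in section 5 for continuous data is also on the raw scale: "continuous data using N, min, Q1, median, Q3, max, and mean (STD) (when appropriate) and 95% CI". Nowhere does the SAP mention a log scale, a geometric mean or a transfer ratio for each serotype. Item i names no test between arms.

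**The concern.** A ratio is asymmetric on the raw scale. A serotype with half the maternal level in the infant and one with twice the level average to 1.25, and so do the same two ratios turned upside down. The measure can therefore show infants above mothers, or mothers above infants, from the same data. The more the ratios scatter, the larger the upward pull.

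The median option in section 5.4 acts on the distribution over pairs. By then each pair's eight ratios have already been averaged on the raw scale. The option also leaves the reported statistic to the data: the SAP gives no criterion for normality and does not say whether it is judged by arm or on all arms together.

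Two readings are at stake. A transfer ratio near or above 1 could be reported when transfer is typically lower. And, if scatter is not the same in all arms, part of a difference between vaccine and placebo could come from scatter. Section 1 says that summaries of the secondary outcome measures will be posted publicly, so the figures will be read as they stand.

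**Working it through.** The SAP gives no expected ratio, SD or sample-size calculation for this measure, so there is no stated figure to reproduce. From the SAP come the eight serotypes (section 3.2) and at least 100 evaluable pairs per arm (section 3.1). All SDs, the true ratio of 0.80 and the within-pair correlation of 0.3 below are assumptions.

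**Direction.** For any set of positive ratios the arithmetic mean is at least the geometric mean, with equality only if all are equal. This holds in every pair, so both the mean and the median of the pair averages are at least as large as the same statistic computed from the pair geometric means. No assumption on the distribution is needed.

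**Size on means.** For log-normal ratios with standard deviation s of the log ratio, arithmetic mean / geometric mean = exp(s²/2):

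- s = 0.2: exp(0.020) = 1.02
- s = 0.3: exp(0.045) = 1.05
- s = 0.4: exp(0.080) = 1.08
- s = 0.5: exp(0.125) = 1.13
- s = 0.7: exp(0.245) = 1.28

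**Effect of the median option.** A simulation of 200,000 pairs with eight serotypes and a true geometric mean ratio of 0.80 gave:

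| s, all serotypes | Mean of pair averages | Median of pair averages | Geometric mean ratio |
|---|---|---|---|
| 0.3 | 0.84 | 0.82 | 0.80 |
| 0.5 | 0.91 | 0.86 | 0.80 |
| 0.7 | 1.02 | 0.93 | 0.80 |

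At s = 0.7 the median removes (1.023 − 0.928)/(1.023 − 0.80) = 43% of the excess. The rest stays.

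**Comparison between arms, with equal true transfer.** The inflation factors cancel if s is the same in both arms: 1.28/1.28 = 1. If s is 0.7 in placebo, placebo appears higher by 1.278/1.133 = 1.13 when the vaccine arm has s = 0.5, and by 1.278/1.083 = 1.18 when it has s = 0.4. With medians, 0.7 against 0.5 gives 0.928/0.862 = 1.08.

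**What a test would do.** The SAP names none, so this only illustrates scale. With 100 pairs per arm, equal true ratios and a nominal 5% level (3,000 repetitions), the false-positive rates were:

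| s: vaccine / placebo | t-test on raw averages | Rank test on raw averages | t-test on log averages |
|---|---|---|---|
| 0.3 / 0.3 | 5.7% | 5.0% | 5.3% |
| 0.3 / 0.5 | 55% | 25% | 6% |
| 0.3 / 0.3, but two serotypes at 0.7 in placebo | 34% | 13% | 5% |

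**Weight of noisy serotypes.** If two of eight serotypes have s = 0.7 and six have 0.3, the two supply 59% of the variance of the raw average and 49% on the log scale, against an equal share of 2/8 = 25%. At s = 1.0 the figures are 80% and 60%. The log scale lessens this but does not cure it.

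**The case against.** The strongest reply is that the arithmetic mean ratio is a legitimate parameter in its own right and not a miscalculated geometric mean. To call 0.5 and 2.0 neutral already presumes the log scale. That is fair: the SAP contains no wrong figure here, and the point is a better choice of method. It still stands as such, because a parameter that changes its message when numerator and denominator are swapped is a poor measure of transfer.

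Second, this is one of six secondary objectives, item i is descriptive, and primary conclusions are untouched. That limits the weight of the point. But the objective is worded as a comparison with placebo, and arm estimates with confidence intervals will be read as one.

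Third, section 1 leaves table outlines and coding descriptions to the Analysis Implementation Plan, which is not at hand and may name a scale. If it does, the SAP text should be brought into line with it.

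A reader might go further and infer that the arm comparison is biased, or that low-level serotypes near the assay limit drive it. The SAP does not support either. It gives no serotype concentrations, variances, assay limit or expected placebo levels. Bias between arms needs lower placebo levels, greater scatter at low levels, and a material difference in scatter by arm. Each is plausible; none is documented.

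**Conclusion.** The point holds as an improvement in method. The planned measure lies at or above the geometric mean by construction, and the median option shrinks the gap without closing it. The direction is certain; the size is not known from the SAP. On means it would be 2% to 5% at log-SDs of 0.2 to 0.3 and 28% at 0.7, assuming log-normal ratios.

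Distortion of the vaccine-versus-placebo comparison is conditional. It is about zero with equal scatter, and 13% to 18% on means if the log-SD is 0.4 to 0.5 in the vaccine arms and 0.7 in placebo. For 0.7 against 0.5 it is about 8% on medians. The 13% to 18% is the result of chosen inputs and should not be quoted as an expected bias.

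**What to change.** In sections 3.2 and 5.4, item i, define the measure on the log scale:

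- For each serotype, compute log(infant) − log(mother) at birth/delivery, and average these logs over the eight serotypes within each pair.
- Report geometric mean ratios with 95% CI by arm, for each serotype and across serotypes.
- Report the ratio of the geometric mean ratios, each vaccine arm to placebo, with 95% CI.
- Delete the choice between mean and median.

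The results by serotype also show whether a few noisy serotypes dominate the overall figure, which the log scale alone does not prevent.

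Excluding serotypes with low maternal values should not be the main remedy. If it is run, it should be labelled a sensitivity analysis that selects on a value measured after vaccination and may remove more placebo data than vaccine data.

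The cost is SAP wording and the matching table layout. Samples and assay results stay the same.
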